### **Time to clinical response**

Clinical response is defined as the NEWS score <=2 maintained for 24 hours from Day 1 through Day 29. The time to the first occurrence of clinical response will be estimated using the Kaplan-Meier (KM) method. The KM estimates along with 95% CI, and survival curves will be provided. Based on the KM estimates, the probabilities of achieving first clinical response and associated 95% CIs on Days 15 and 29 will be reported; in addition, the 25th, 50th (median), and 75th percentiles of the time to first clinical response with associated 95% CIs will be provided, as data permit. The survival rates between treatment groups will be compared using Log-rank test. The p-value from Log-rank test will be presented.

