The NEWS has demonstrated an ability to discriminate patients at risk of poor outcomes. This score is based on 7 clinical parameters (respiration rate, oxygen saturation, any supplemental oxygen, temperature, systolic blood pressure, heart rate, level of consciousness [Alert, Voice, Pain, Unresponsive]).

<https://www.mdcalc.com/national-early-warning-score-news> (Appendix 2)

- Time to clinical response: NEWS ≤ 2 maintained for 24 hours, Day 1 through Day 29

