All subjects will be followed daily through Day 10. After Day 10, if subjects are discharged from the hospital, evaluations at Day 15 and 29 are required. Berlin criteria for ARDS ([Appendix 3](#)) and SOFA score ([Appendix 4](#)) will be assessed on Day 1, 5, 15, and 29. Subjects remaining hospitalized will be followed daily through Day 29. Days 15±1 and 29±1 may be performed at the study site or, if deemed appropriate, at an alternate site (e.g., subject's residence, local healthcare professional's site) under the care and supervision of trained healthcare personnel. If an in-person visit is unable to be conducted for Day 15 or

GRIFOLS Bioscience Industrial Group	Number	BLG-CL-PR7-000020	Version	4.0	Status	Effective	Effective Date	19-Jul-2021
	GC2007 - A Multicenter, Randomized, Open-label Parallel Group Pilot Study to Evaluate Safety and Efficacy of High Dose Intravenous Immune Globulin (IVIG) plus Standard Medical Treatment (SMT) versus SMT alone in						Page	34 of 91

Day 29, the study site will make a phone call to the subject to obtain as much information as possible remotely (e.g., Ordinal Scale, clinical features key symptoms, supplementation oxygen use, SAEs and TEAEs, concomitant medications). Phone Checks will occur at Day 60 and Day 90 for vital status (living or deceased), any hospital re-admissions or serious/non-serious adverse events after the Day 29 Final Clinic Visit. Details are provided in [Appendix 1](#) (Schedule of Study Procedures). Clinical status will be evaluated for all hospitalized subjects daily with vital signs, Ordinal Scale (7 categories analogous to Cao et al. 2020), and NEWS at Screening/Baseline and during IVIG plus SMT or SMT alone treatment and during Follow-up. The NEWS calculation is delineated in [Appendix 2](#) and can be calculated using the on-line web tool at <https://www.mdcalc.com/national-early-warning-score-news> .

For subjects in the combination arm (IVIG plus SMT) all laboratory samples must be drawn prior to infusion of IVIG, if laboratory assessments are required for a day in which IVIG is being infused.

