7.2.5 Day 15±1 day – All Subjects

Day 15±1 day may be performed at the study site or, if deemed appropriate, at an alternate site (e.g., subject's residence, local healthcare professional's site) under the care and supervision of trained healthcare personnel. If an in-person visit is unable to be conducted for Day 15, the study site will make a phone call to the subject to obtain as much information as possible remotely (e.g., Ordinal Scale, clinical features key symptoms, supplementation oxygen use, SAEs and TEAEs, concomitant medications).

Assessments include the following:

- Ordinal Scale assessment
- NEWS ([Appendix 2](#))
- Clinical features key symptoms: fever, cough, shortness of breath, fatigue, myalgia etc.
- Vital signs (temperature, systolic and diastolic blood pressure, pulse, respiratory rate)
- Record any supplemental oxygen administration (type, %, flow start/end date/time)
- Record details of mechanical ventilation parameters (start/end date/time)
- Record oxygen saturation (specify on or off oxygen supplementation)
- Assessment of ARDS (Berlin Criteria) ([Appendix 3](#))
- SOFA score ([Appendix 4](#))
- Respiratory sample for quantitative measurement of SARS-CoV-2 viral load by NAT or PCR (real-time RT-PCR) (obtained via nasopharyngeal swab)
- Sample for quantitative measurement of IgM and IgG antibodies to SARS-CoV-2 (store serum samples frozen at -70°C for later analysis at an external lab)
- Serum Chemistry (creatinine, albumin, ALT, total bilirubin, LDH)
- Ferritin (serum), D-dimer (plasma, sodium citrate tube), CRP (serum)
- Hematology absolute lymphocyte count and standard hematology (hemoglobin, hematocrit, platelet count, leukocyte count with differential)
- DAT
- Cytokine panel (IL-1 β , IL-10, IL-6, IL-8, IL-2, interferon γ , and TNF- α). Note: serum samples must be stored at -70°C for later analysis at a reference laboratory.
- Record SAEs and TEAEs
- Record standard care concomitant medications

GRIFOLS Bioscience Industrial Group	Number	Big-CL-PRT-000020	Version	4.0	Status	Effective	Effective Date	19-Jul-2021
	GC2007 - A Multicenter, Randomized, Open-label Parallel Group Pilot Study to Evaluate Safety and Efficacy of High Dose Intravenous Immune Globulin (IVIG) plus Standard Medical Treatment (SMT) versus SMT alone in							

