Appendix 2 National Early Warning Score (NEWS)

The NEWS has demonstrated an ability to discriminate patients at risk of poor outcomes. This score is based on 7 clinical parameters (respiration rate, oxygen saturation, any supplemental oxygen, temperature, systolic blood pressure, heart rate, level of consciousness [Alert, Voice, Pain, Unresponsive]). To calculate you may access <https://www.mdcalc.com/national-early-warning-score-news>

Details are also provided below.

Formula: Addition of the selected points; points assigned below:

Criteria	Point Value
Respiratory Rate (breaths per minute)	
≤8	+3
9-11	+1
12-20	0
21-24	+2
≥25	+3
Oxygen Saturation (%)	
≤91	+3
92-93	+2
94-95	+1
≥96	0
Any Supplemental Oxygen	
Yes	+2
No	0
Temperature in °C (°F)	
≤35.0 (95)	+3
35.1-36.0 (95.1-96.8)	+1
36.1-38.0 (96.9-100.4)	0
38.1-39.0 (100.5-102.2)	+1
≥39.1 (≥102.3)	+2

GRIFOLS		Number	BIG-CL-PRT-000020	Version	4.0	Status	Effective	Effective Date	19-Jul-2021	Page	82 of 91												
GC2007 - A Multicenter, Randomized, Open-label Parallel Group Pilot Study to Evaluate Safety and Efficacy of High Dose Intravenous Immune Globulin (IVIG) plus Standard Medical Treatment (SMT) versus SMT alone in																							
Systolic BP																							

 
 ≤90	+3	
 
 91-100	+2	
 
 101-110	+1	
 
 111-219	0	
 
 ≥220	+3	
 
												≤90	+3	91-100	+2	101-110	+1	111-219	0	≥220	+3		
≤90	+3																						
91-100	+2																						
101-110	+1																						
111-219	0																						
≥220	+3																						
Heart Rate (beats per minute)																							

 
 ≤40	+3	
 
 41-50	+1	
 
 51-90	0	
 
 91-110	+1	
 
 111-130	+2	
 
 ≥131	+3	
 
												≤40	+3	41-50	+1	51-90	0	91-110	+1	111-130	+2	≥131	+3
≤40	+3																						
41-50	+1																						
51-90	0																						
91-110	+1																						
111-130	+2																						
≥131	+3																						
AVPU																							

 
 A	0	
 
 V, P, or U	+3	
 
												A	0	V, P, or U	+3								
A	0																						
V, P, or U	+3																						

AVPU, Alert, Voice, Pain, Unresponsive.

Interpretation:

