**Table 1 Missing Data and Competing Events Coding for Time to Event Data Analyses**

Endpoint	Right Censoring and Competing Events
Subject Survival	Subjects who are still alive as of the last known follow-up will be right censored as of the date of last subject contact when the subject was known to be alive.
Time to actual ICU Discharge or Medical Equivalence of ICU Discharge (if different from actual ICU discharge date)	Subjects who did not discharge or medical equivalence of discharge from the ICU at any time during follow-up will be right censored as of the date of last subject contact when the subject was known to be in the ICU. Subject death will be considered a competing event. Competing risk methods e.g., cumulative incidence function (CIF) will be used to account for competing events in the analysis.
Time to actual Hospital Discharge or Medical Equivalence of Hospital Discharge (if different from actual hospital discharge date)	Subjects who did not discharge or medical equivalence of discharge from the hospital at any time during follow-up will be right censored as of the date of last subject contact when the subject was known to be in the hospital. Subject death will be considered a competing event. Competing risk methods e.g., cumulative incidence function (CIF) will be used to account for competing events in the analysis.
Time to Clinical Response	Subjects who did not experience clinical response or died at any time during follow-up will be right censored as of the date of last non-missing assessment of NEWS on or prior to Day 29.

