#### 4.6 Data Derivations and Transformations

The following derivations will be used in this study:

Study Day:

- Date of assessment – date of randomization + 1 for assessments done on or after date of randomization
- Date of assessment – date of randomization for assessments done before date of randomization

Baseline Observation: the last non-missing value prior to randomization.

Duration:

- Duration in days = end date – start date + 1
- Duration in minutes = end time in minutes – start time in minutes

Origin or Start Date for Time to Event Endpoints:

- Time to death: date of randomization
- Time to ICU Discharge (actual and medical equivalence, if applicable): date of randomization or date of ICU admission, whichever was later
- Time to Hospital Discharge (actual and medical equivalence, if applicable): date of randomization
- Time to Clinical Response: date of randomization

Event Date for Time to Clinical Response:

- If a subject met the criteria for clinical response at multiple assessments, the date of the first assessment meeting the definition of clinical response will be used as the event date for deriving time to clinical response.

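### Time to clinical response has no rule for live discharge: a subject sent home after Day 10 before 24 hours of NEWS ≤2 are documented is censored or stays event-free

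*SAP*

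**What the plan says.** Protocol 4.1.2 lists the endpoint as "Time to clinical response: NEWS ≤ 2 maintained for 24 hours, Day 1 through Day 29". SAP 6.2 repeats it: "Clinical response is defined as the NEWS score <=2 maintained for 24 hours from Day 1 through Day 29". The analysis is Kaplan-Meier from randomization with a log-rank test. If the criterion is met more than once, SAP 4.6 says that "the date of the first assessment meeting the definition of clinical response will be used as the event date". Neither document says which recorded scores establish the 24 hours.

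Under SAP 4.4, Table 1, a subject without a response is "right censored as of the date of last non-missing assessment of NEWS on or prior to Day 29". The row for this endpoint does not mention discharge.

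Protocol 7.2.4, 7.2.6 and Appendix 1 restrict daily NEWS on Days 11–14 and 16–28 to inpatients. For the others, Protocol 4.2 says: "After Day 10, if subjects are discharged from the hospital, evaluations at Day 15 and 29 are required". If the Day 15 visit cannot be held in person, "the study site will make a phone call to the subject to obtain as much information as possible remotely" (Protocol 7.2.5; 7.2.7 says the same for Day 29). The examples given for that call name neither NEWS nor vital signs. Appendix 2 says of NEWS: "This score is based on 7 clinical parameters", and most of these are physical measurements. The SAP is based on protocol version 3.0 (SAP 1), before the telephone fallback was added, and does not address it.

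On Days 2–10 the text conflicts. Protocol 4.2 has every subject followed daily up to Day 10, and Appendix 1 marks NEWS on those days without an inpatient condition. The design paragraph of the synopsis limits daily assessment to the hospital stay and sees discharged subjects on Days 15 and 29. Protocol 4.2 itself also describes daily NEWS as being for hospitalized subjects.

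**The concern.** The endpoint is meant to capture recovery, and going home alive is one of its clearest signs. Yet discharge after Day 10 ends the daily scores needed to show that a low NEWS has lasted 24 hours. A subject whose NEWS first reaches 2 on the day of discharge leaves no second reading the next day.

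If no later NEWS exists, the subject leaves the risk set at discharge, and Kaplan-Meier assumes that future response would match that of the unresolved subjects who remain. Since recovery is what led to discharge, that assumption fails. If a Day 29 NEWS exists but is not accepted as proof of 24 hours, the subject counts as at risk and unresponsive to the end. At stake are the estimated response probabilities, the power of a secondary comparison in a trial of about 100 subjects, and whether two programmers would derive the same result.

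**Working it through.** No figure for this endpoint is stated and the sample size has no calculation behind it, so there is nothing to reproduce. The check has two parts.

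**1. Applying the rules to example subjects.** Each has NEWS above 2 until the day named.

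- NEWS ≤2 on Days 11 and 12, discharged Day 13: two consecutive daily scores exist. This subject is a responder and is unaffected.
- NEWS 2 on Day 12, discharged that day, Days 15 and 29 by telephone without NEWS: right censored at Day 12.
- Same course, with NEWS ≤2 in person on Days 15 and 29: if single scores do not prove 24 hours, event-free and censored at Day 29. If the Day 12 and Day 15 scores are read together as maintained, a responder.

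The last two subjects recovered identically, and the SAP permits three codings between them.

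**2. Illustrative size.** Inputs from the documents: about 100 subjects randomized 1:1, two-sided 5% log-rank test, Kaplan-Meier, deaths right censored for this endpoint. Assumptions not in the documents: 60% recover and 30% die by Day 29 in the control arm, with constant hazards; the hazard ratio for response is 1.7; a share f of recoveries in both arms is discharged unconfirmed.

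Total daily hazard = −ln(1 − 0.90)/28 = 0.0822. Recovery hazard = 0.0822 × 0.60/0.90 = 0.0548. With deaths censored, Kaplan-Meier response at Day 29 = 1 − exp(−28 × 0.0548) = 0.785. This exceeds 0.60 because deaths are censored.

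Simulation, 50 per arm, 1,500 runs (control-arm Kaplan-Meier from the runs with no treatment effect; power at hazard ratio 1.7):

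| f | Day 29 response: discharge counted / censored at discharge / event-free to Day 29 | Power, same order |
|---|---|---|
| 0.1 | 0.783 / 0.746 / 0.689 | 0.58 / 0.54 / 0.39 |
| 0.2 | 0.785 / 0.708 / 0.610 | 0.59 / 0.49 / 0.29 |
| 0.4 | 0.786 / 0.599 / 0.444 | 0.60 / 0.37 / 0.17 |

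The Monte Carlo standard error of a power near 0.5 is √(0.25/1500) = 0.013, so 0.58 to 0.60 are one value within error. With no treatment effect and equal f, rejection under the two current-rule codings was 0.043 to 0.054.

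Cross-check by the Schoenfeld formula, power = Φ(√(d/4) × ln 1.7 − 1.96), with d = 60(1 − f): 0.54 for d = 60, then 0.50, 0.45 and 0.36 for d = 54, 48 and 36. The simulated powers under censoring at discharge run slightly higher because the simulation has more events (61, 55 and 41). Censoring at discharge loses power mainly through lost events. The event-free coding also pulls the curves together.

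**How large f could be.** If every subject has daily NEWS through Day 10, the only unconfirmed recoveries are those first seen on Day 10 or later. In this model their share of control-arm recoveries is (exp(−8 × 0.0822) − 0.10)/0.90 = (0.518 − 0.100)/0.90 = 0.46. Then f = 0.4 would need 0.40/0.46, about 86%, of them to leave unconfirmed, so it is an extreme. The lower rows are easier to believe unless daily NEWS also stops at discharge on Days 2–10.

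**The case against.** The strongest reply is that the plan is silent rather than wrong. The documents do not limit NEWS to one reading a day. The SAP does not bar accepting a discharge-day score and a Day 15 score as maintained. The telephone items are only examples. Subjects with 24 hours documented before discharge lose nothing, and discharge has its own secondary endpoint, analysed by cumulative incidence and Gray's test. All of this stands, and it means the number affected is unknown and could be small. It does not supply a rule: a subject discharged less than 24 hours after the first NEWS ≤2 still has no guaranteed confirming score.

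A reader might also infer more than the documents support:

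- *That NEWS stops at every discharge.* This is clear only after Day 10; for Days 2–10 the text conflicts.
- *That these subjects are scored as non-responders.* Table 1 censors them. They are non-responders in effect only when a later NEWS keeps them at risk.
- *That the analysis is biased against IVIG.* This needs more unconfirmed discharges in the IVIG arm. Nothing in the documents gives the share in either arm.
- *That a subject sent home with NEWS 3 is a missed responder.* That subject has not met the stated definition. Counting discharge broadens the endpoint.
- *That an Ordinal-scale floor is needed because supplemental oxygen scores only 2 points and NEWS has no ventilation item.* An alert subject on support can indeed have NEWS 2. But a floor at category 4 is debatable and would still admit a stable subject on low-flow oxygen with NEWS 2 at baseline.

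**Conclusion.** The point holds in limited form. After Day 10, a subject discharged alive before 24 hours of NEWS ≤2 are documented is either informatively censored or left event-free, and the SAP does not say which. Response is understated and power is lost. With f from 0.1 to 0.4, control-arm Day 29 response falls by 0.04 to 0.19 if such subjects are censored at discharge and by 0.09 to 0.34 if they stay event-free to Day 29. These sizes rest on the assumed recovery, death and hazard ratio figures and on f, none of which the documents give.

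With equal loss in both arms and no treatment effect, the test keeps its level. Bias between arms remains conditional on unequal loss. The matter concerns one secondary endpoint of a pilot study and does not touch the mortality analysis. It is a cheap improvement to make before the data are analysed.

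**What to change.** In SAP 4.4 Table 1, 4.6 and 6.2, define the event as the first of:

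- (a) NEWS ≤2 on two consecutive daily post-baseline assessments, stating which of the two readings dates the event; or
- (b) live hospital discharge, dated at discharge, stating that the actual rather than the medical-equivalence date is meant.

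Keep the NEWS-only definition as a sensitivity analysis, with explicit rules for isolated Day 15 and Day 29 scores and for telephone visits without NEWS. Reconcile the protocol text on whether subjects discharged by Day 10 have daily NEWS.

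The cost is SAP wording and one derivation, with no new data, since discharge dates are already recorded. Because the definition also stands in the protocol, record the change in an amendment and/or the clinical study report, as Protocol 9.5 provides. The downside is more overlap with time to hospital discharge, so the result should be described as NEWS response or discharge.

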5 SELECTION AND WITHDRAWAL OF SUBJECTS

5.1 Inclusion Criteria

A subject must meet all the following inclusion criteria to be eligible for participation in this study:

1. Hospitalized male or female subjects of ≥ 18 years of age at time of Screening who are being treated in the ICU for COVID-19 for not longer than 48 hours or for whom a decision has been made that COVID-19 disease severity warrants ICU admission.
2. Has laboratory-confirmed novel coronavirus (SARS-CoV-2) infection as determined by qualitative PCR (reverse transcriptase [RT]-PCR), or other FDA-approved-or regulatory-

GRIFOLS Bioscience Industrial Group	Number	BLG-CL-PRT-000020	Version	4.0	Status	Effective	Effective Date	19-Jul-2021	41 of 91
	GC2007 - A Multicenter, Randomized, Open-label Parallel Group Pilot Study to Evaluate Safety and Efficacy of High Dose Intravenous Immune Globulin (IVIG) plus Standard Medical Treatment (SMT) versus SMT alone in						Page		

authority-approved diagnostic assay for COVID-19 in any specimen during the current hospital admission prior to randomization.

3. Illness (symptoms of COVID-19 of any duration requiring ICU level care), and the following:
 - a) Radiographic infiltrates by imaging (chest X-Ray, CT scan, etc.), AND
 - b) Requiring mechanical ventilation and/or supplemental oxygen.

Note: ICU level care is defined as the medical need for intensive or invasive monitoring; immediate or impending need for supportive care of the airway, breathing, or circulation; and/or stabilization of acute severe or life-threatening complications of COVID-19.
4. Any one of the following related to COVID-19: i. Ferritin > 400ng/mL, ii. LDH > 300 U/L, iii. D-Dimers > reference range, or iv. C-reactive protein (CRP) > 40 mg/L.
5. Subject provides informed consent prior to initiation of any study procedures.

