After all Screen/Baseline assessments are complete subjects may be randomized.

Subjects in the combination arm may receive the first infusion of Gamunex-C on Screen/Baseline and Randomized Treatment visit (Day 1) if eligibility criteria are met, and all pre-infusion assessments are performed. Subjects in the combination arm will receive a total of 2 g/kg Gamunex-C in divided doses. At the prerogative of the Principal Investigator the 2 g/kg dose may be divided into 4 days (500 mg/kg/day) or 5 consecutive days (400 mg/kg/day).

Vital signs will be monitored during Gamunex-C infusion. Vital signs will be measured within 1 hour prior to the start of Gamunex-C infusion, 30 minutes after the start of infusion, and hourly through the end of Gamunex-C infusion. If the systolic blood pressure measured within 1 hour prior to the start of Gamunex-C infusion is > 160 mm Hg, then measures to lower blood pressure below this threshold should be administered and documented prior to commencing Gamunex-C infusion. To commence the Gamunex-C infusion, the systolic blood pressure must be < 160 mm Hg.

7.2.3 SMT, Randomized IVIG Treatment, Daily Evaluations (Days 2 through 10 inclusive) and Additional Day 5±1 Day Assessments

All subjects receive continued SMT. Subjects randomized to IVIG plus SMT will receive the remainder of the net 2 g/kg dose in divided doses at the Principal Investigator's prerogative on consecutive days through Day 4 (500 mg/kg/day) or through Day 5 (400 mg/kg/day) to achieve the total dose of 2 g/kg body weight. Subjects receiving Gamunex-C infusions will have vital signs measured within 1 hour prior to the start of each Gamunex-C infusion, 30 minutes after the start of infusion, and hourly through the end of Gamunex-C infusion. If the systolic blood pressure measured within 1 hour prior to the start of Gamunex-C infusion is > 160 mm Hg, then measures to lower blood pressure below this threshold should be administered and documented prior to commencing Gamunex-C infusion. To commence the Gamunex-C infusion, the systolic blood pressure must be < 160 mm Hg.

Daily assessments include the following:

- Ordinal Scale assessment
- NEWS ([Appendix 2](#))
- Clinical features key symptoms: fever, cough, shortness of breath, fatigue, myalgia etc.
- Vital signs (temperature, systolic and diastolic blood pressure, pulse, respiratory rate)
- Record any supplemental oxygen administration (type, %, flow start/end date/time)

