### **Assessment of clinical severity**

The NEWS will be calculated based on 7 clinical parameters and recorded on the eCRF. The absolute value and change from baseline in the total score from Day 1 through Day 29 will be summarized by treatment group and visit using descriptive statistics.

Change in NEWS total score through Day 29 will be evaluated by fitting a linear MMRM. The model will include change from baseline in NEWS total score as the repeated dependent variable; treatment (as a class variable), visit (as a class variable), and treatment-by-visit interaction as fixed effects; baseline NEWS total score, age and gender as covariates; and measures within subject at each visit as a repeated measure. An unstructured covariance matrix will be used to model the within-subject error. If the fit of the unstructured covariance structure fails to converge, a compound symmetry covariance structure will be used. Parameters will be estimated using restricted maximum likelihood with the Kenward-Roger method for calculating the denominator degrees of freedom. Data collected starting at the Day 2 visit and up to the Day 29 visit will be included in this analysis. Missing data will not be imputed. From this model, the least-squares (LS) means and 95% CIs for each treatment group, the treatment difference in the LS means, the 95% CI for the difference, and the associated p-value will be reported on Days 15 and 29, as well as for the average across all post-baseline visits.

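### Clinical response (NEWS of 2 or less for 24 hours) is not limited to post-randomisation scores, so a subject who enters with NEWS 2 can be counted as a responder without improving.

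*SAP*

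**What the plan says.** SAP section 6.2 (Time to clinical response) defines the endpoint: "Clinical response is defined as the NEWS score <=2 maintained for 24 hours from Day 1 through Day 29". The first occurrence is analysed by Kaplan-Meier with a log-rank test. Response probabilities at Days 15 and 29 and the three quartiles of time to response are to be reported.

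SAP section 4.6 sets the clock. The origin is given as "Time to Clinical Response: date of randomization". If several assessments qualify, "the date of the first assessment meeting the definition of clinical response will be used as the event date". Study day is "Date of assessment – date of randomization + 1 for assessments done on or after date of randomization", so a NEWS taken on the day of randomisation is a Day 1 value even if it was taken before randomisation.

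Protocol section 7.2.2 lists NEWS among the Day 1 screening and baseline procedures and adds: "After all Screen/Baseline assessments are complete subjects may be randomized". The schedule in protocol Appendix 1 shows the Day 1 NEWS in the screening/baseline column and none in the first-infusion column.

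Protocol section 5.1, criterion 3b, sets the respiratory entry requirement: "Requiring mechanical ventilation and/or supplemental oxygen". Sections 5.1 and 5.2 set no minimum NEWS. Appendix 2 gives 2 points for "any supplemental oxygen", whatever the device or flow, and has no item for ventilation, inspired oxygen fraction or vasopressors.

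Neither document says how 24-hour maintenance is to be shown from daily scores, or how subjects already at NEWS 2 or less at baseline are handled.

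**The concern.** A time-to-response endpoint is informative only if subjects are not yet responders when the clock starts. Here the window includes the baseline measurement, and nothing in the entry criteria guarantees that subjects start above the threshold. A subject who enters on oxygen with otherwise normal observations and stays the same for a day can be recorded as a responder. Because the first occurrence counts, later deterioration does not undo the event.

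The threshold also does not require freedom from organ support. An alert subject still on ventilation or vasopressors can reach NEWS 2 if every other item is normal.

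Such events tell us little about treatment. They add noise to the log-rank statistic and pull the reported quartiles towards zero.

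**Working it through.** **1. What NEWS allows.** The documents state no response rate, event count or power for this endpoint, so there is no figure to reproduce. The check is to enumerate the Appendix 2 bands. Respiratory rate has 5 bands, oxygen saturation 4, temperature 5, systolic pressure 5 and heart rate 6, giving 5 × 4 × 5 × 5 × 6 = 3000 combinations for each state of oxygen use and consciousness.

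| Supplemental oxygen | Consciousness | Minimum NEWS | Combinations with NEWS ≤2 |
|---|---|---|---|
| Yes (+2) | Alert (0) | 2 | 1 of 3000 |
| Yes (+2) | V, P or U (+3) | 5 | 0 of 3000 |
| No (0) | Alert (0) | 0 | 32 of 3000 |
| No (0) | V, P or U (+3) | 3 | 0 of 3000 |

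The single qualifying combination on oxygen is respiratory rate 12–20, saturation 96% or more, temperature 36.1–38.0 °C, systolic pressure 111–219 mm Hg, heart rate 51–90 and alert: 0 + 0 + 2 + 0 + 0 + 0 + 0 = 2. These counts show what is possible, not how often it happens.

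**2. From score to event.** Take a subject with that profile on Days 1 and 2. The Day 1 score precedes randomisation. The Day 2 score shows that NEWS of 2 or less has lasted about 24 hours, so the definition is met. Section 4.6 then dates the event either to Day 1 (the first score in the qualifying run) or to Day 2 (the score at which maintenance is shown). Either way the subject is a responder with no change in NEWS.

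**3. Number affected, on assumed shares.** Let f be the share of each arm counted this way. The documents do not give f. With 50 per arm, 50f = 2.5, 5 or 10 subjects for f = 5%, 10% or 20%. If f is taken as the share with baseline NEWS of 2 or less, these are upper bounds, because the score must also hold on Day 2.

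**4. Effect on the log-rank test, on assumed inputs.** Assumptions: 50 per arm, 50% control response by Day 29 with a constant rate, no deaths or dropout, two-sided 5% level, 3000 simulated trials per case (Monte Carlo standard error at most √(0.25/3000) = 0.9 percentage points), affected subjects set as Day 1 events in both arms. The last two columns exclude those subjects, using power = Φ(½·√d·ln HR − 1.96). Here d is the expected number of events at f = 0 (57.4 at HR 1.5, 62.4 at HR 2.0) times (1 − f).

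| f | Counted, HR 1.5 | Counted, HR 2.0 | Excluded, HR 1.5 | Excluded, HR 2.0 |
|---|---|---|---|---|
| 0 | 32% | 79% | 34% | 78% |
| 5% | 31% | 72% | 32% | 76% |
| 10% | 25% | 68% | 31% | 74% |
| 20% | 22% | 56% | 28% | 69% |

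At f = 0 the two methods should agree, and they do. For f above 0, the fair comparison is counted against excluded on the same row, because exclusion does not restore the full sample. At HR 2.0 the gap is about 4, 6 and 13 points.

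**5. Effect on the Kaplan-Meier quartiles, same assumptions.** With a share f responding at time zero, the control-arm time at which a proportion q has responded is t = 28·ln[(1 − f)/(1 − q)]/ln 2 days.

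| f | 25th percentile | Median |
|---|---|---|
| 0 | 11.6 days | 28.0 days |
| 5% | 9.5 days | 25.9 days |
| 10% | 7.4 days | 23.7 days |
| 20% | 2.6 days | 19.0 days |

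The lower quartile is the most sensitive.

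**The case against.** Several stronger readings are tempting, and the documents do not support them.

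- **That the Day 1 score alone is enough.** It is not. The score must be maintained for 24 hours, so a post-randomisation score has to confirm it. The Day 1 score can begin a qualifying run, and on one reading date it.
- **That events are necessarily dated before treatment.** Section 4.6 can equally be read as dating the event to the confirming score. The ambiguity is itself a gap, but a Day 1 date is not a settled fact.
- **That ventilated subjects in general can be responders.** Anyone scored V, P or U, for example through sedation, has NEWS of at least 3, and at least 5 on oxygen. A subject recorded as on oxygen must be alert with every other item at zero.
- **That some events certainly are not recoveries.** In a population needing ICU-level care, a full day of otherwise normal observations may be rare. The documents give no baseline NEWS distribution, so they support only that some events may not be recoveries.
- **That the treatment comparison is biased.** Baseline NEWS is fixed before randomisation, so baseline responders are balanced between arms in expectation.

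Two further objections have force. The repeated-measures model for NEWS does exclude the baseline score ("Data collected starting at the Day 2 visit and up to the Day 29 visit will be included in this analysis"), but it analyses change from baseline and had to start later, so the contrast proves little. Recovery from organ support is also measured elsewhere: time to medical equivalence of ICU discharge, duration of mechanical ventilation and the Ordinal scale. A NEWS response on support is therefore not a contradiction, and making an Ordinal category part of the main definition would be a trade-off rather than a correction.

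What stands is that the response is not restricted to post-baseline scores, subjects already at the threshold are not handled, and 24-hour maintenance is not defined.

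**Conclusion.** The concern holds in a limited form. As written, SAP sections 6.2 and 4.6 allow a subject who enters with NEWS 2 and stays there to be counted as a responder, and an alert subject on ventilation or vasopressors with otherwise normal values could also qualify. This follows from the definition, the Day 1 schedule, the absence of a minimum NEWS at entry and the Appendix 2 scoring.

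The size is unknown, because the documents do not give the share affected. On the assumed inputs above, the loss of log-rank power is small at 5% and material at 20%, and the lower quartile of time to response shifts at every assumed share. The consequence is dilution and distorted descriptive percentiles for one secondary endpoint, in a pilot trial with no power calculation and no multiplicity adjustment. The primary mortality analysis is untouched. The change is worth making because it is cheap.

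**What to change.** 1. In SAP sections 6.2 and 4.6, count only post-baseline NEWS (Day 2 onward). Define 24-hour maintenance as two consecutive daily scores of 2 or less, and say which of the two dates the event. Add a rule for subjects discharged before a second score. After Day 10, discharged subjects are seen only at Days 15 and 29, either visit may be replaced by a phone call, and the protocol's examples of what to collect by phone do not include NEWS.
2. Report the number with baseline NEWS of 2 or less by arm, and repeat the log-rank analysis without them. Starting at Day 2 is not enough by itself, because it only moves their event by about a day. The exclusion uses a pre-randomisation value, so the comparison remains randomised.
3. As a sensitivity analysis only, require Ordinal category 4 or better on both days.

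The cost is SAP wording and a little extra analysis. NEWS and the Ordinal scale are already recorded daily in hospital. The downside is slightly fewer events, including some around discharge that cannot be confirmed.
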